#### 9.4 Main Secondary Outcomes

As described in Section 9.3, the PHC/Mortality and LV mass/Mortality composites are the coprimary endpoints for evaluation of patient benefit in the trial. In addition, as described in Section 5.1.2, main secondary outcomes have also been designated for each of seven specific and conceptually distinct physiological or quality of life-related outcome domains. These include: i) change over 12 months in the PHC; and, ii) change over 12 months in LV mass (without the mortality components), which represent the main secondary outcomes for evaluation of the physical function and cardiac structure and function domains, respectively. The remaining outcome domains and associated main secondary outcomes are iii) depression/disease burden (change over 12 months in Beck Depression Inventory), iv) nutrition (change over 12 months in serum albumin), v) cognitive function (change over 12 months in the Trail Making Test B), vi) mineral metabolism (change over 12 months in average pre-dialysis phosphorus), and vii) clinical events (rate of nonaccess hospitalizations or death). The primary evaluation of the effects of the treatment interventions on each of these seven outcome domains will be based on the designated main secondary endpoints. Analyses of other outcomes within each domain will be regarded as exploratory. Hypertension and anemia are also stipulated as main outcome domains, but are not conducive to the designation of a single main endpoint.

Two-sided tests will be used when testing the effects of the interventions on both the primary and secondary endpoints. The primary and main secondary analyses will be conducted by intention-to-treat in the sense that all patients analyzed according to their randomized assignment, irrespective of whether they adhered to the interventions. As noted above, however, follow-up will be censored at the time of renal transplantation. The analyses of the main secondary endpoints will be tested at the 0.05 level, without formal adjustment for multiple comparisons. However, nominally significant

effects on individual secondary outcomes will be interpreted as consistent with Type I errors unless accompanied by significant effects of the interventions on the primary outcomes and a consistent pattern of treatment effects across multiple secondary outcomes.

### 9.5 General Analytic Strategy for Quantitative Outcomes

The following analytic strategy will be employed for quantitative outcomes, including each of the main secondary outcomes with the exception of the rate of nonaccess hospitalization or death. The main analysis for each outcome will evaluate the treatment effect on the change from baseline to 1 year. For outcomes evaluated monthly (e.g., serum albumin and pre-dialysis phosphorus), the baseline value will be averaged over two baseline assessments and the 1 year value will be averaged over the Month 10, 11, and 12 assessments for increased statistical power. For each outcome with multiple follow-up assessments (including the PHC, serum albumin, Beck Depression Inventory, Trail Making Test B, and pre-dialysis phosphorus), an additional analysis will be conducted to evaluate the change from baseline to Month 4, where the Month 4 value is taken as the average value over months 3, 4, and 5 for serum albumin and pre-dialysis phosphorus. The analysis of change to 4 months will evaluate short term effects, while the analysis of change to 1 year will evaluate longer-term effects. The 4-month comparison is also intended to evaluate treatment effects prior to significant attrition. The "basic model" to be used for quantitative outcomes is:

$$\Delta Y_{t} = \beta_{0t} + \beta_{1t} \operatorname{Trt} + \beta_{2t} Y_{0} + \Sigma \gamma_{it} S_{i} + \Sigma \delta_{it} F_{i} + \varepsilon_{t}, \qquad (Basic Model)$$

where  $\Delta Y_t$  denotes the change in the response variable from baseline to time t, Trt is an indicator variable for the daily treatment intervention,  $Y_0$  is the baseline value of the response variable, the  $S_i$ are indicator variables for the Clinical Centers, the  $F_i$  are the two pre-specified baseline covariates age, and diabetic status, and the  $\varepsilon_t$  are random residuals at t=4 and 12 months. The primary focus of the model will be to estimate the treatment effect  $\beta_{1t}$  as accurately as possible; the remaining terms are included to reduce residual variability and reduce bias from missing data. The model will be fit by restricted maximum likelihood (Harville 77) assuming an approximate normal distribution and with an unstructured covariance matrix for the residuals at the two time points. The change in the LV mass from baseline to its single follow-up assessment at 12 months will be analyzed by restricting the basic model to one time point, which simplifies to traditional analysis of covariance. In addition to evaluating the effects of the treatment interventions on LV mass, in grams, the effects of the interventions on the percentage change in LV mass will also be considered in secondary analyses.

The target sample size of 250 patients is sufficient that inferences for the fixed effect terms in these analyses will remain valid with moderate departures from normality (Verbeke 97). However, standard diagnostics will be performed and simulations conducted to address this issue, and modifications to the model will be made if necessary.

# 9.6 Analysis of Non-Access Hospitalization Rate or Death

The effects of the treatment interventions on the rate of non-access hospitalizations or death will be analyzed by treating the non-access hospitalizations and death as correlated event-time outcomes under a semi-parametric survival analytic framework. An Anderson-Gill model for recurrent events will be used to characterize the effects of the interventions on the intensity rate for the non-access hospitalizations, and a Cox-proportional hazards model will be used to characterize the effects of the interventions on the hazard rate for mortality. The joint analysis of both outcomes will be stratified by type of outcome (non-access hospitalization vs. mortality) to allow for potential differences between the baseline hazard function for mortality and the baseline intensity function for non-access hospitalizations. The models for both outcomes will be stratified also by Clinical Center, with treatment group and the pre-specified covariates included as independent variables. A common treatment effect will be modeled for both outcomes in order to produce a pooled estimated treatment effect across the two outcomes. Standard errors will be estimated using robust "sandwich-type" estimates to account for correlations in (possibly) multiple events within the same patient. Follow-up time will be censored at death for the non-access hospitalization outcome and at time of transplantation, transfer to a nonparticipating dialysis facility, or the end of the 12-month follow-up period for both the non-access hospitalization and death outcomes. Censoring at transplant and transfer to nonparticipating dialysis units is necessary because hospitalizations will not be recorded or classified following these events. The incorporation of death as a separate event in addition to nonaccess hospitalizations is intended, in part, to reduce the risk of bias due to informative censoring.

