# 3.2 Duration of Treatment and Follow-up

Each subject will be treated in his or her respective group for 12 months, or until death, a treatment stop-point is met, or loss to follow-up (see Section 7.3). The complete data collection procedures of the protocol will continue for the full 12 month follow-up period except for those subjects who die or are lost to follow-up. For subjects who relocate to a non-study dialysis unit, all attempts will be made to collect vital status, the primary and main secondary outcomes (see Section 5.1.2), and other centrally administered quality of life questionnaires at the 12-month assessment. When possible, the complete data collection procedures designated in the protocol will be maintained for subjects who switch to home HD. Those patients who are transplanted or switch to peritoneal dialysis will no longer be followed. Otherwise, no matter what happens to a patient, it is recommended that all attempts be made to encourage any subject who misses the two co-primary outcomes to provide these data for up to six months past his or her F12 window. Adverse events hospitalizations and serious adverse events should be recorded for an additional 30 days after the patients' F12 month ends. Starting with the first dialysis session held at least 30 days after the patients' F12 month ends, one week of data should be recorded from the dialysis unit's run sheets. This data will include start time, end time, and pre and post weight and blood pressure for each dialysis session held during the week.

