#### 7.4 Losses to Follow-up

Efforts will be made to follow all randomized subjects for 12 months, irrespective of their adherence to the randomized therapy. However, certain situations may preclude complete data collection for the full 12 months (losses to follow-up).

The randomized therapy and routine data collection will be discontinued in the following situations:

- a. Subject withdraws consent for data collection
- b. Subject changes to peritoneal dialysis
- c. Subject receives renal transplant
- d. Subject relocates to a non-study center.
- e. Subject changes to home HD.

For patients who are lost to routine data collection for reasons b - e above, all attempts will be made to collect vital status. For patients who are lost to routine data collection for reasons d and e above, all attempts will be made to collect vital status, the primary and main secondary outcomes, and other centrally administered quality of life questionnaires at the 12-month visit.

All losses to follow-up with reason will be reported to the DCC (discontinuation of therapy form). The Adherence Committee will review all losses to follow-up on a monthly basis.

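### Section 9.6 leaves peritoneal dialysis and consent withdrawal out of its censoring list, and censors deaths at transfer for a reason that covers only hospitalizations

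*Protocol*

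**What the plan says.** Section 9.6 models non-access hospitalizations as recurrent events (Andersen-Gill) and death by Cox regression. The joint analysis is stratified by outcome type and fits one common treatment effect. Hospitalization is censored at death. Beyond that, follow-up is censored at "transplantation, transfer to a nonparticipating dialysis facility, or the end of the 12-month follow-up period for both the non-access hospitalization and death outcomes". The reason given is: "Censoring at transplant and transfer to nonparticipating dialysis units is necessary because hospitalizations will not be recorded or classified following these events".

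Section 7.4 has a longer list of events that end recording. It opens "The randomized therapy and routine data collection will be discontinued in the following situations" and names five. Besides transplant and relocation to a non-study center, these are (a) "Subject withdraws consent for data collection", (b) "Subject changes to peritoneal dialysis" and (e) "Subject changes to home HD". Section 3.2 agrees about peritoneal dialysis: "Those patients who are transplanted or switch to peritoneal dialysis will no longer be followed".

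On deaths, Section 7.4 adds: "For patients who are lost to routine data collection for reasons b - e above, all attempts will be made to collect vital status". Section 3.2 likewise seeks vital status after relocation. In Section 9.3 the co-primary composites are censored before month 12 only at transplant or when mortality follow-up is lost; transfer alone does not censor.

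**The concern.** The censoring list in 9.6 looks complete, but it is shorter than the list of events after which hospitalizations go unrecorded. A recurrent-event model needs each patient's risk time to end when events can no longer be seen. If it does not, the remaining months enter as months without a hospitalization. That lowers the estimated rate in each arm in proportion to its exits, and it distorts the treatment ratio if exits differ between arms.

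The second problem runs the other way. Death is censored at transfer on a ground that concerns only hospitalization records, while the trial plans to keep seeking vital status. Section 9.6 says death was included partly to limit bias from informative censoring, and discarding known deaths works against that aim. A death after transfer would count in the co-primary composites but not here.

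The outcome affected is the main secondary outcome for the survival and hospitalization domain.

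**Working it through.** **Events side by side**

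| Event | Routine recording of hospitalizations | Vital status sought | Censors in 9.6 |
|---|---|---|---|
| Transplant | stops (3.2, 7.4c) | yes in 7.4; 3.2 says not followed | yes, both outcomes |
| Transfer | stops (7.4d, 9.6) | yes (3.2, 7.4) | yes, both outcomes |
| Peritoneal dialysis | stops (3.2, 7.4b) | yes in 7.4; 3.2 says not followed | not listed |
| Consent withdrawal | stops (7.4a) | not among b to e | not listed |
| Home HD | stops in 7.4(e); continues where possible in 3.2 and after a stop point in 7.3(b) | yes (7.4) | not listed |

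Peritoneal dialysis and consent withdrawal are clear gaps. Home HD is a contradiction: under 3.2 and 7.3(b) it is right not to censor, under 7.4(e) it is not.

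**The plan's own figure**

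Section 9.11 states a minimum detectable reduction of 39% at 80% power and 45% at 90%. Inputs: 125 per arm (250, 1:1), 1.19 hospitalizations per year plus 0.12 deaths per year, and two-sided 0.05. The average follow-up fraction of 90% is an assumption.

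- Control events: 125 × 1.31 × 0.90 = 147.4. With a 39% reduction the daily arm has 89.9, total 237.3.
- Poisson standard error of the log ratio: √(1/147.4 + 1/89.9) = 0.134.
- Standard error needed for 80% power: −ln(0.61)/(1.960 + 0.842) = 0.176.
- Implied variance inflation: (0.176/0.134)² = 1.74. The same steps for 45% and 90% power give 1.78.

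Poisson variance alone would give detectable reductions of 30.3% and 34.6%. The protocol states no between-patient dispersion, so its figures cannot be reproduced exactly. However, the two imply nearly the same, plausible inflation. Nothing here shows them to be wrong, and the censoring gap does not change them.

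**Effect of unrecorded time**

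Let a share q of an arm stop recording at times spread evenly over the year, with a constant hospitalization rate, while staying in the risk set. On average half a year of events is missed for each such patient, so the arm's rate is under-counted by q/2. With a true ratio of 1:

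observed ratio = (1 − q_daily/2) / (1 − q_conv/2)

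| q daily | q conventional | Observed ratio |
|---|---|---|
| 2% | 2% | 1.000 |
| 5% | 2% | 0.975/0.990 = 0.985 |
| 10% | 5% | 0.950/0.975 = 0.974 |
| 10% | 2% | 0.950/0.990 = 0.960 |
| 20% | 2% | 0.900/0.990 = 0.909 |

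All q values are assumptions. The only nearby figures come from the earlier hemodialysis trial used for planning: about 18% lost to death, transplant and transfer (9.9) and about 80% in active follow-up at one year (9.11). That leaves roughly 100 − 80 − 18 = 2% for every other reason. These are rounded figures from a different trial. The ratios above apply to the hospitalization component, which supplies 1.19/1.31 = 91% of expected events, so the pooled estimate would move slightly less.

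**Effect of discarding deaths after transfer**

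Expected deaths at 12% per year in both arms: 250 × (1 − e^−0.12) = 28.3. Deaths dropped: 250 × transfer share × 0.5 year × 0.12 per year. Taking 18% − 12% − 4% = 2% as a rough transfer share, and 4% and 6% as higher assumptions:

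- 2%: 0.3 deaths
- 4%: 0.6 deaths
- 6%: 0.9 deaths

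**The case against.** Section 9.6 never says that patients remain at risk once recording stops. Its stated reason for censoring points toward censoring at peritoneal dialysis and withdrawal as well, and a careful analyst would probably do so, perhaps under an analysis plan not seen here. This stands in part: the defect is an omission, not a decision to count unobserved time. But the protocol states a specific list that does not match its own follow-up rules, and its text is what would be followed.

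A reader might infer that burn-out on daily HD makes the error favor the daily arm. The documents do not support that. Sections 7.1 and 7.3(a) keep patients who reduce or abandon the assigned schedule in data collection, so those returning to conventional in-center HD still have their hospitalizations recorded. Burn-out creates unrecorded time only through peritoneal dialysis or withdrawal of consent (and home HD if 7.4(e) governs). Exclusion criterion 10 in Section 2.5.2 also removes patients already scheduled to change to peritoneal dialysis or home HD.

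On deaths, a shared follow-up window is defensible when one treatment effect is pooled over both outcomes, and ascertainment after transfer may be incomplete because vital status is only sought. That bears on the size of the problem. It does not supply the missing reason, and Section 9.3 already relies on the same information.

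**Conclusion.** The point holds as a mismatch between a stated censoring rule and the protocol's own data-collection rules, on a main secondary outcome. Peritoneal dialysis and consent withdrawal should end hospitalization risk time and are not listed. Home HD is unresolved between Sections 3.2 and 7.3(b) on one side and 7.4(e) on the other. Deaths after transfer are censored without a reason that applies to them.

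The likely effect is small. The rate ratio is undisturbed if exits are equal between arms, and moves to about 0.985 at 5% versus 2% or 0.960 at 10% versus 2%. These figures assume even timing of exits, a constant rate and exit shares that the protocol does not give. Exits of 10% to 20% in the daily arm would matter more, but nothing in the document supports such rates, and the direction is not established. Fewer than one of about 28 expected deaths would be lost at transfer shares up to 6%. Section 9.4 further limits the consequences by treating isolated secondary findings as consistent with chance.

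It is worth correcting because the correction is easy, not because the trial's conclusions depend on it.

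**What to change.** In Section 9.6, replace the common censoring rule with one for each outcome:

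- **Hospitalization:** censor at death, at month 12, or on the date hospitalization recording stops for any reason. Name transplant, transfer, peritoneal dialysis and consent withdrawal, and add home HD only if reconciliation confirms that collection stops there.
- **Death:** censor only at transplant, last known vital status or month 12, consistent with Section 9.3.

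Reconcile Sections 3.2, 7.3(b) and 7.4(e) on data collection after a move to home HD. Also reconcile 3.2 with 7.4 on whether vital status is sought after peritoneal dialysis or transplant.

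The cost is two sentences in 9.6 plus the reconciliation. No new data are needed, and no new method: the model is already stratified by outcome type, so each outcome can carry its own censoring time. The change should be made before any comparison by treatment arm, so that the rule is not chosen after seeing results.

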## 9.7 Analysis Strategies for Other Outcomes

A modified version of the basic model for Bernoulli response variables will be used to analyze the change in the rates of dichotomous outcomes such as the presence of intra-dialytic hypotensive episodes [Diggle, 1994]. Primary unassisted patency will be defined as the time from randomization until the first access procedure or thrombosis (including angioplasty), and analyzed by Cox regression stratified by Clinical Center with treatment group and the pre-specified covariates as independent variables [Klein, 1997].

Ordinal variables will be analyzed using longitudinal models adapted for ordinal categorical outcomes with repeated measurements [Liang, 1995;Toledano, 1999].

## 9.8 Additional Analyses of the Effects of the Interventions

In addition to considering effects of the interventions on outcome at 4 and 12 months, contrasts will be constructed to estimate their effects on the change from 4 to 12 months to determine if treatment effects are changing over time. For quantitative outcomes obtained monthly, the basic model will be extended to evaluate patterns of change incorporating each protocol time point. Due to the larger number of time points, the covariance matrix of the residuals will be estimated under a mixed effects model including random effects (e.g., a random intercept and slope) and additional correlation parameters as needed to fit the serial correlation structure of the data [Littell, 1996;Verbeke, 1998].

Concentrations of serum albumin, hematocrit, and hemoglobin as well as blood pressure and body weight may shift shortly after initiation of daily dialysis due to altered extracellular volume, complicating interpretation of longitudinal changes. Thus, we plan to supplement tests of effects of the treatment interventions on changes from baseline to month 4 or month 12 (which may overestimate beneficial effects of the daily intervention due to hemoconcentration) with contrasts evaluating the changes from the month 1 visit, at which time most hemoconcentration effects should have occurred. Contrasts for changes from baseline to the month 1 visit will be used to estimate the size of the change in extracellular water and the associated hemoconcentration effects.

Analyses will also be used to test for interactions between the treatment interventions and prespecified baseline factors to evaluate whether certain subgroups experience increased or reduced benefits of the interventions. The Steering Committee has pre-specified the following factors for evaluation of treatment interactions:

History of heart disease, gender, anthropometric volume (Watson volume < 35 L vs.  $\ge 35$  L), years of dialysis (< 4 years vs.  $\ge 4$  years), presence of residual renal function (defined by > 100 mL urine volume per 24 hours).

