#### 2.4 Recruitment Strategy

The target sample size for this trial is 250 subjects, half of whom will be randomized to in-center daily HD. Subjects will be recruited from dialysis units associated with designated Clinical Centers affiliated with the two Consortium Cores. Within each of the Clinical Centers, persons receiving conventional 3 times weekly HD in the associated HD units will be potential study subjects. Currently, these dialysis units provide clinical services to > 7500 prevalent HD patients. It is estimated that approximately 50% of prevalent HD patients will be eligible for enrollment, based on inclusion and exclusion criteria. Resource and logistical constraints (e.g., available stations) may limit the numbers of subjects for whom the protocol can be implemented concurrently at a given site. Local efforts will be concentrated on those dialysis units and referring nephrology programs with large numbers of patients and adequate physical space. Under this staggered enrollment strategy, fewer than 50% of the total number of randomized subjects will be in the trial at any given time, thus easing the time required to implement the protocol for personnel conducting the study.

The progress of recruitment into this trial and into the companion nocturnal dialysis trial will be reviewed by the Data Safety and Monitoring Board (DSMB) at the conclusion of the one year Vanguard phase. Depending on the progress of the two trials, their target sample sizes may be modified.

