# 2.8 Randomization of Trial Participants

Once the baseline evaluation is completed and eligibility is verified, consenting subjects will be randomly allocated in a 1:1 allocation to conventional or daily HD. The randomization schedules will be prepared by the Data Coordinating Center (DCC) prior to the start of recruitment.

Randomization will be stratified by Clinical Center and by diabetes status. Randomly permuted blocks of random sizes will be used to help balance numbers of participants assigned to both treatment regimens. This method guarantees that at no time during randomization will the participants in the individual groups be grossly unequal.

The randomization process will be centrally administered. All randomization schedules will remain confidential and known only by members of the Data Coordinating Center staff.

Once all baseline period studies have been completed, the forms corresponding to these studies have been received by the Data Coordinating Center, and the forms have been checked to be sure the patient meets eligibility requirements, the Principal Investigator or the study coordinator shall access the interactive randomization program. The program will verify through a defined set of questions that the participant is eligible and ready to be randomized and provide a randomized treatment assignment for that participant based upon his or her stratum. The randomization assignment will be displayed on the screen and emailed to the Clinical Center.

Randomization marks the participant's official and irrevocable entry into the Follow-up Period. Once a participant has been randomized, efforts will be made to conduct all evaluations irrespective of whether the subject starts the study treatment regimen or not, how long the patient continues on the

study treatment regimen, and how well the patient adheres to the study treatment regimen (see Section 7). These efforts should continue until termination of the Follow-up Period.

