The minimum detectable treatment effects under the above assumptions were estimated by statistical simulation, and are presented in Table 15a. Note that under Hochberg's procedure the threshold used to test the significance of each of the two co-primary endpoints depends on the other; hence, as indicated in the table, the minimum detectable effect size for the PHC/Mortality composite depends in part on the magnitude of the treatment effect on LV mass, and the minimum detectable effect size for the LV mass/Mortality composite depends on the size of the treatment effect on the PHC. Under a hypothesized treatment effect leading to a 20% reduction in the mortality rate, the target sample size of 250 patients has 90% power to detect treatment effects ranging from 4.59 to 4.96 points for the change in SF-36 PHC score, depending on the size of the treatment effect on LV mass. Similarly, the study has 90% power to detect treatment effects ranging from 12.1 to 13.3g for the change in LV mass, depending on the size of the treatment effect.

Table 15b provides the estimated minimum detectable effect sizes for each of the quantitative main secondary outcomes under the following assumptions: a) measurements obtained at 12 months in 80% of patients for each outcome, b) the standard deviations of the changes in each outcome (with covariate adjustment) are as indicated in the table, c) two-sided significance levels of 0.05 are applied to each outcome, without adjustment for multiple tests, d) utilization of the parametric analysis of changes with covariate adjustment as outlined in Section 9.5. The power calculations do not take into

Outcome	Treatment Effect on Other Primary Outcome 	80% power	90% power	
	0	11.3 g	13.0 g	
LVmass - Mortality	2.28 g	10.9 g	12.6 g	
	4.56 g	10.3 g	12.1 g	
	0 units	4.28 units	4.96 units	
PHC - Mortality	6 units	4.12 units	4.80 units	
	12 units	3.91 units	4.59 units	

Table 15a

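### Section 9.8 tests treatment interactions with body water volume and years of dialysis as two-group factors; continuous terms would keep more information if the effect changes gradually

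*Protocol*

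**What the plan says.** Section 9.8 announces the analysis in these words: "Analyses will also be used to test for interactions between the treatment interventions and prespecified baseline factors". Its purpose there is to see whether some subgroups gain more or less than others. The Steering Committee names five factors. History of heart disease and gender are categorical. The other three rest on measured quantities and are cut in two:

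- "anthropometric volume (Watson volume < 35 L vs" 35 L or more;
- "years of dialysis (< 4 years vs" 4 years or more;
- "presence of residual renal function (defined by > 100 mL urine volume per 24 hours").

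The section gives no reason for the cut-points, no version with the continuous value and no power for an interaction test. Power is stated only for main effects (section 9.11, Tables 15a and 15b) and for the rate of non-access hospitalization or death.

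**The concern.** A two-group term treats every patient on one side of the cut as alike. A patient at 36 L counts the same as one at 50 L, while patients at 34 L and 36 L count as different. If benefit rises or falls steadily with body size or time on dialysis, the within-group part of that gradient is not used. The tests are imprecise to begin with, so a real gradient becomes still easier to miss. Section 9.10 looks ahead to a later full-scale trial, for which such a gradient would be useful planning information.

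For volume, the protocol's own figures show gradual change. Table 4 (section 3.1.2) gives the eKt/V that corresponds to the daily-arm target at each volume, and it falls steadily from 1.01 at 25 L through 0.90 at 35 L to 0.80 at 50 L. That is a statement about dose per V, not about benefit, but it makes a gradient at least as natural a hypothesis as a step.

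**Working it through.** **Inputs.** Section 2.4: "The target sample size for this trial is 250 subjects, half of whom will be randomized to in-center daily HD". Section 2.8: "consenting subjects will be randomly allocated in a 1:1 allocation to conventional or daily HD". Section 9.11: "measurements obtained at 12 months in 80% of patients for each outcome", which gives 250 × 0.80 = 200 patients, 100 per arm. Section 9.11 also says "two-sided significance levels of 0.05 are applied to each outcome, without adjustment for multiple tests"; that is stated for the main secondary outcomes and is assumed here for the interaction tests. Standard deviations from Table 15b: PHC 8.310 points, LV mass 24.00 g.

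**1. Reproduce the protocol's figures.** Detectable main effect at 80% power = (1.960 + 0.842) × SD × √(2/100).
- PHC: 3.29 by the normal formula, 3.31 by the t distribution; Table 15b says 3.31.
- LV mass: 9.51 g and 9.56 g; Table 15b says 9.6 g.

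The inputs are therefore read correctly.

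**2. Precision of a two-group interaction.** With a share p of patients in one subgroup, SE = SD × √(4 / (200 p(1−p))).
- Even split, PHC: 8.310 × √(4/50) = 2.35, so the detectable difference between subgroup effects is 2.80 × 2.35 = 6.58 points.
- Even split, LV mass: 19.0 g.

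Both are about twice the detectable main effect. An interaction as large as the detectable main effect has about 29% power at an even split: 3.31/2.35 = 1.41, and Φ(1.41 − 1.96) = 0.29. It has about 25% at 70/30 and 20% at 80/20.

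**3. Information kept by a cut.** If the treatment effect is linear in the modifier X, the relative efficiency of the split is the squared correlation of X with its group indicator:
- normal X: φ(c)² / (p(1−p)), which is 2/π = 0.637 at the median;
- uniform X: 3p(1−p), which is 0.75 at the median.

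Starting from 80% power on the continuous scale, power after the split is Φ(2.80 × √efficiency − 1.96).

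| Modifier (assumed) | Split | Kept | Lost | Power left of 80% |
|---|---|---|---|---|
| Uniform | 50/50 | 0.75 | 25% | 68% |
| Uniform | 60/40 | 0.72 | 28% | 66% |
| Uniform | 70/30 | 0.63 | 37% | 60% |
| Normal | 50/50 | 0.637 | 36% | 61% |
| Normal | 60/40 | 0.622 | 38% | 60% |
| Normal | 70/30 | 0.576 | 42% | 57% |
| Normal | 80/20 | 0.490 | 51% | 50% |
| True step at the cut | any | 1 | 0% | 80% |

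For right-skewed modifiers (exponential, gamma with shape 2, lognormal with log-SD 0.7), cut anywhere from the 30th to the 70th percentile, the loss ranged from 36% to 73%. That assumes an effect linear in the untransformed value.

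**4. Check by simulation.** With 200 patients, a normal modifier, a least-squares interaction t-test and 4,000 runs per setting, 79% power fell to 58% (50/50) and 54% (70/30). Power of 29% fell to 21% and 19%. This agrees with the formula to within about 3 points.

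**5. Where 35 L comes from.** The dose scaling is V_n = 3.271 × V^(2/3) (section 3.1.1). V_n equals V when V = 3.271³ = 35.0 L. At the 0.90 target, eKt/V = 0.90 × 3.271 × V^(−1/3), which gives 1.01 at 25 L and 0.80 at 50 L, as in Table 4. The curve is smooth through 35 L.

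**The case against.** The best case for the plan has four parts.

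- **The 35 L cut is not arbitrary.** It is where V_n and V coincide, so it separates patients dosed above 0.90 per V from those dosed below, and residual clearance is also expressed per 35 L. This stands as an explanation of where the number comes from. It does not make 35 L a response threshold, since dose per V passes through it smoothly. No comparable origin is given for 4 years.
- **The cuts are fixed in advance and match a question about subgroups.** This stands. A reader might infer from the word cut-point that the groups could be chosen after seeing results; the protocol rules that out. What remains is that the result depends on which cut was fixed.
- **The gain is limited.** This stands. An interaction that has 29% power after an even split would have about 42% on the continuous scale for a normal modifier (1.41/√0.637 = 1.77, and Φ(1.77 − 1.96) = 0.42). A reader might infer that the change makes these tests reliable; it does not.
- **A continuous term needs a functional form.** This stands too. A wrong form can miss a threshold or a non-monotone pattern, and section 9.8 does not forbid a supplementary continuous analysis. But the section does choose the two-group form for the tests, so this is a stated method rather than a detail left open.

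One factual limit: Watson volume is computed per patient (sections 3.1.3 and 3.1.5), but the protocol does not say how time on dialysis is recorded. A duration or start date is presumably needed to form the 4-year groups.

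**Conclusion.** The point holds as a minor improvement. If the treatment effect changes about linearly with the modifier, the two-group tests give up about a quarter of the information in the mildest case examined (uniform, cut near its median). They give up 36 to 42% for a normal modifier split between 50/50 and 70/30, and possibly more if years of dialysis is skewed. In power terms, 80% becomes about 61% or 57% in the two normal cases.

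A reader might infer that more than a third of the information is lost whatever the circumstances. The protocol does not support that: it gives neither the distribution of either modifier nor the share of patients on each side of either cut, and a true step at the cut would cost nothing. Nor does the point reach the trial's main conclusions. These are additional analyses, and no co-primary test, main secondary test or sample-size figure depends on them.

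**What to change.** In section 9.8, state that the interaction test for Watson volume and for years of dialysis uses the continuous value, in one form named in advance (for example linear volume and log years), entered with its main effect and its product with treatment in the model for the outcome concerned. That is the section 9.5 model for quantitative outcomes and the section 9.6 model for non-access hospitalization or death. Keep the 35 L and 4-year groups for displaying subgroup estimates. The same could be considered for urine volume.

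The log-rank comparison of the co-primary composites carries no modifier term. If interactions are wanted there, a regression counterpart has to be named whichever form the modifier takes.

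The cost is a sentence or two, with the same number of tests and no new volume data. The downside is that a form must be fixed beforehand and a non-linear effect could be missed; the displayed groups help to reveal that.
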